5.7.3 Clinical Laboratory Evaluation

5.7.3.1 Hematology and Chemistry

Hematology and chemistry safety parameters are measured at Visits 1, 3, 5 and 7. Summaries will be presented by treatment group for each laboratory parameter at each visit for the safety analysis set. Change from baseline and percent change from baseline to each post-baseline visit will also be presented.

If values for any of the parameters are below or above the limit of quantification of the assay (BLQ or ALQ), then they will be included in the summary tables at the BLQ or ALQ thresholds. However, for estimated creatinine clearance, results >60 are reported only as '>>60'. Hence, estimated creatinine clearance (CrCl) will be calculated using the Cockcroft-Gault equation:

$$\text{CrCl (mL/min)} = [(140 - \text{age}) \times \text{weight} \times k] / \text{serum creatinine}$$

where age is measured in years, weight is measured in kg, k = 1.23 if male, k = 1.04 if female and serum creatinine is measured in $\mu\text{mol/L}$.

CrCl will be indexed to body surface area (BSA) using the following formula:

$$\text{Corrected CrCl (mL/min/1.73m}^2\text{)} = \text{CrCl (mL/min)} \times 1.73/\text{BSA}$$

where BSA is based on the Du Bois and Du Bois formula:

$$\text{weight}^{0.425} \times \text{height}^{0.725} \times 0.007184$$

where weight is measured in kg and height is measured in cm.

When available, enzymatic serum creatinine will be used. Otherwise, the Jaffe serum creatinine will be used. If height or weight is missing at the collection date, then the closest value to the sample date will be used. If there is more than one height or weight value on the same day or 2 height or weight values equally distant from the collection date, then the mean will be used.

Where laboratory samples are repeated, the baseline value is defined as the final recorded value prior to the first dose of IMP.

Shift tables for hematology and biochemistry parameters will be constructed, based upon normal ranges and GW toxicity limits (See Section 8), to determine the categorical shifts from baseline to each post-baseline visit in the treatment period. Values will be categorized as 'Normal', 'Low' or 'High' based on normal ranges and 'Toxicologically Low', 'Toxicologically Normal' or 'Toxicologically High' based on GW toxicity limits.

For CrCl, results will be assigned to the following grades:

- Normal: $>60 \text{ ml/min/1.73 m}^2$
- Grade 1: $60 \text{ ml/min/1.73 m}^2$
- Grade 2: $\geq 30 \text{ and } < 60 \text{ ml/min/1.73 m}^2$
- Grade 3: $\geq 15 \text{ and } < 30 \text{ ml/min/1.73 m}^2$
- Grade 4: $< 15 \text{ ml/min/1.73 m}^2$

A separate shift table will be produced for CrCl based upon the above grades to determine the categorical shifts from baseline to each post-baseline visit.

Table will be produced summarizing the number of participants meeting the following criteria:

- Alanine aminotransferase (ALT) $> 1 \times \text{ULN}$ at baseline
- Aspartate aminotransferase (AST) $> 1 \times \text{ULN}$ at baseline
- AT $> 1 \times \text{ULN}$ at baseline
- Treatment emergent ALT $> 3 \times \text{ULN}$, $> 5 \times \text{ULN}$ and $> 8 \times \text{ULN}$
- Treatment emergent AST $> 3 \times \text{ULN}$, $> 5 \times \text{ULN}$ and $> 8 \times \text{ULN}$
- Treatment emergent AT $> 3 \times \text{ULN}$, $> 5 \times \text{ULN}$ and $> 8 \times \text{ULN}$
- Treatment emergent AT $> 3 \times \text{ULN}$ and either bilirubin $> 2 \times \text{ULN}$ or INR > 1.5

where AT is AST or ALT, and treatment emergent is defined as criteria not met at baseline but met at any time post-baseline. The above will be summarized overall and for sex (male, female).

All laboratory data will be listed; listings will include limited demographic information about the participant (age, sex, race and weight at baseline). Abnormal laboratory values will be listed separately. A further listing will be created for the laboratory reference ranges and toxicity limits. A listing of liver parameters (ALT, AST, bilirubin and INR) will be produced that includes the baseline result, result at the particular visit, change from baseline, upper limit of normal (ULN) value, ratio of result to baseline and ratio of result to ULN.

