PP Per protocol

PRN Packaging reference number

PVD Pharmacovigilance Department

QTcF QT interval with Fridericia correction

RNA Ribonucleic acid

RTSM Randomization and Trial Supply Management

SAE Serious adverse event
SAP Statistical analysis plan

SCI-PANSS Structured Clinical Interview Positive and Negative Symptoms

Scale

SOC System organ class

SUSAR Suspected unexpected serious adverse reaction

SQLS Schizophrenia Quality of Life Scale

TBL Total bilirubin

TD Tardive dyskinesia

TEAE Treatment-emergent adverse event

THC Δ^9 -tetrahydrocannabinol

TRH Thyrotropin-releasing hormone

ULN Upper limit of normal

US United States

WOCBP Women of childbearing potential

Confidential Page 26 of 104

EudraCT Number: 2019-003369-16 Clinical Protocol Global V3, 23Mar2021

Definition of Terms

Term	Definition
Day 1	The day a participant first receives investigational medicinal product during the treatment period in this trial.
End of trial	Last participant last visit or last contact, whichever occurs last.
Enrolled participant	Any participant who has provided written informed consent to take part in the trial.
International normalized ratio	A calculation made to standardize prothrombin time.
Investigational medicinal product	Term used to describe both investigational active product and reference therapy (placebo).
Investigator	Trial principal investigator or a formally delegated trial physician.
QT interval	A measure of the time between the start of the Q wave and the end of the T wave in the heart's electrical cycle.

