13.4 General Considerations

Unless stated otherwise, continuous variables will be summarized showing the number of non-missing values (n), mean, SD, median, minimum, and maximum, and categorical variables will be summarized showing the number and percentage of participants falling in each category. Unless otherwise specified, tables will be summarized by randomized treatment group.

For clinic visit-based endpoints (unless otherwise specified), baseline is defined as the last record or measure collected prior to the first dose of IMP in the treatment period.

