- h. An ECG will be performed after 5 minutes in a supine position, if possible. The ECGs should be done in triplicate at screening and baseline to ensure that QTcF < 450 msec (males)/ < 470 msec (females). Any subsequent ECG should be done once and should be repeated 2 times in cases where withdrawal criteria are met (QTcF ≥ 500 msec).
- i. To include HIV, hepatitis B, and hepatitis C.
- j. Plasma concentrations of the background antipsychotic medications will be assessed at Visit 1 and predose relative to the administration of IMP at Visit 4 and Visit 7.
 - CBD and its major circulating metabolites will be assessed at Visit 1 and relative to the administration of IMP at Visits 4 and 7. A PK sample will be collected before the participant's morning dose of IMP and within 12 hours (-3/+6 hours) since last IMP dose (Visit 4 and Visit 7). Following collection, the IMP will be administered with a meal of at least 300 kcal to be provided. At Visit 1, only a baseline PK sample will be collected. At Visit 4 and Visit 7, samples to determine concentrations of CBD and its major circulating metabolites will be collected pre- and postdose, relative to IMP, at a timepoint between 2 to 3 hours. Thereafter optional PK sampling may be collected at postdose time points between 4 to 6 hours and 8 to 10 hours.
- k. A drug screen test (urine) will include alcohol, amphetamines (including ecstasy), barbiturates, benzodiazepines, cocaine, methadone, opiates, and THC. THC will be blinded from Visit 3 to the end of the trial.
- 1. Assessment to be conducted prior to dosing of any regular medication prescribed for the management of extrapyramidal side effects (e.g., anticholinergics, beta-blockers etc.).
- m. Every effort should be made to include informant information in the PANSS assessment through administration of the Informant Questionnaire PANSS. If contact with a participant's informant cannot be made within 3-day window from the date of the study visit, either by phone or in person, then the informant interview should not be considered a barrier to visit progression.
- n. IMP is to be taken orally b.i.d., (e.g., morning and evening) preferably within 30 minutes of a meal using the syringe(s) provided. Participants will be asked to return all IMP (used and unused) at each relevant visit. The first dose of IMP at Visit 2 should be taken at the site.

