5.1.2 Day Numbering

The first day of treatment in the treatment period (Day 1) will be taken from 'Date of first dose of IMP in Treatment Period' on the Randomization CRF.

Any days prior to Day 1 will be numbered relative to this day and calculated as:

Date – (Date of Day 1)

to give Day -1, -2, -3 etc.

Any days post Day 1 will be calculated as:

Date - (Date of Day 1) + 1

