5.1.3 Definitions

5.1.3.1 Baseline

For clinic visit-based endpoints, baseline is defined as the last non-missing record or measure collected prior to the first dose of IMP in the treatment period.

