For the summary of TEAEs by time of first onset of AE, data will be summarized for the treatment period separately under the following categories:

- Weeks 1–2 (Day 1 to 14).
- Weeks 3–4 (Day 15 to 28).
- Weeks 5–8 (Day 29 to 56).
- Weeks 9–12 (Day 57 to 84).
- >12 weeks (> Day 84).

The time to first onset of AE in treatment period will be calculated for TEAEs as:

$$\text{Start date of AE} - \text{Date of first dose of IMP in treatment period} + 1$$

If participants have multiple occurrences of an AE then the AE will be counted once for the first occurrence only. Percentages will be based on the number of participants in the safety analysis set who have a visit or follow-up call within each time period above.

For the summary of TEAEs by time to AE resolution, data will be summarized under the following categories:

- 1 week (≤ 7 days).
- 2 weeks (8–14 days).
- 3 weeks (15–21 days).
- 4 weeks (22–28 days).
- >4 weeks (>28 days).
- Ongoing (for AEs not resolved).

The time to AE resolution will be calculated for TEAEs as:

$$\text{Stop date of AE} - \text{Start date of AE} + 1$$

If participants have multiple occurrences of an AE then the AE will be counted once for the occurrence with the longest time to AE resolution. However, if any of the AEs are not resolved then the AE will be counted once within the 'Ongoing' category.

The start and stop day of the AE relative to the first dose of IMP will be calculated as per Section 5.1.2. For partial dates, if it is clear from the partial date that the start/stop day was prior to the first dose of IMP, then 'pre' will be listed, similarly if it is clear that the event was post the first dose of IMP then 'post' will be listed as the start/stop day as appropriate.

Listings will include the start and stop day of the AE, a flag for treatment emergence, and limited demographic information about the participant (age, sex, race and weight at screening).

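### Minor: the SAP's baseline rule for repeated laboratory samples omits the treatment-period qualifier, and its ECG section does not say how the baseline triplicate becomes one analysis value

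*SAP*

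**What the plan says.** **Laboratory baseline.** SAP 5.7.3.1: "Where laboratory samples are repeated, the baseline value is defined as the final recorded value prior to the first dose of IMP". The general rule in SAP 5.1.3.1 is that "baseline is defined as the last non-missing record or measure collected prior to the first dose of IMP in the treatment period", and protocol 13.4 agrees: "baseline is defined as the last record or measure collected prior to the first dose of IMP in the treatment period". The protocol's Definition of Terms counts placebo as IMP, and the schedule of assessments (Appendix 1, footnote n) places the start of dosing in the run-in: "The first dose of IMP at Visit 2 should be taken at the site". On sampling, SAP 5.7.3.1 states: "Hematology and chemistry safety parameters are measured at Visits 1, 3, 5 and 7".

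**ECG baseline.** Protocol Appendix 1 (footnote h) takes ECGs in triplicate at screening and baseline. Later ECGs are single, with two repeats if the QTcF withdrawal criterion is met. Exclusion criterion 6.2.15 judges QTcF at screening or randomization on the mean of three readings, and the QTcF discontinuation criterion in protocol section 10 also uses a mean of three. SAP 5.7.4.2 summarizes ventricular rate, PR, QRS, QT and QTcF by visit, with change from baseline to Day 85 and counts of flagged values. It gives no rule for replicate tracings. Protocol 9.1.10 refers ECG processing to a separate manual, which was not supplied.

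**The concern.** The laboratory sentence is the more specific rule, so a programmer could reasonably apply it in preference to SAP 5.1.3.1. The missing qualifier would not matter in a trial without a run-in. Here it moves the cut-off from Day 1 back to Visit 2, so a value drawn at Visit 3 no longer qualifies as baseline.

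Three kinds of output use the baseline: laboratory change from baseline, the shift tables, and the liver flags. The liver table in SAP 5.7.3.1 calls a criterion treatment-emergent when it was absent at baseline and present at any later time. With a screening baseline, a raised Day 1 transaminase, measured before any GWP42003-P, would count as post-baseline.

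For ECG, the general rule takes the last available record. Read literally, that selects one tracing from the triplicate and ignores the other two. The same silence affects post-baseline flags when tracings are repeated. No efficacy estimate depends on either point.

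**Working it through.** The plan states no figure on this point, so there is nothing to reproduce. The check sets the passages side by side and then sizes the consequence.

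**Labs: what the literal sentence selects**

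1. The first IMP dose is placebo at Visit 2, Day -14 (Definition of Terms; Appendix 1).
2. The only scheduled laboratory draw before that is Visit 1, Day -42 to Day -15 (Appendix 1). A screening retest under protocol 6.2.14 falls in the same window.
3. A repeated-sample baseline is therefore 15 to 42 days before Day 1. Day 85 is 84 days after Day 1, so change to Day 85 spans 84 + 15 = 99 to 84 + 42 = 126 days, against 84 for participants with a Day 1 baseline.
4. Eligible participants have screening ALT and AST no higher than 2 x ULN (protocol 6.2.14). A screening baseline therefore cannot meet the 3 x ULN criterion, and a Day 1 value above 3 x ULN would be classed as treatment-emergent.

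**Labs: size if programmed literally**

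- Randomized: 80 (SAP 3.2). At 2:2:1:1 that is 80 x 2/6, about 27, in each active group and in pooled placebo.
- Share with a repeated sample: 5-20%, assumed; the documents give no rate. 80 x 0.05 = 4 and 80 x 0.20 = 16 participants, about 1 to 5 per group of 27.
- Of those, share with Day 1 ALT or AST above 3 x ULN: 0.5-2%, assumed. Expected number wrongly flagged: 4 x 0.005 = 0.02 to 16 x 0.02 = 0.32.
- Chance of at least one: 1 - 0.995^4 = 0.020 to 1 - 0.98^16 = 0.276, that is 2-28%. This is conditional on the literal reading being programmed and on both assumed rates.

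**Labs: which reading is intended**

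- Protocol 13.6.4.4 lists screening and baseline as separate time points for laboratory summaries.
- SAP Table 2 labels Visit 3 as the baseline visit, and Appendix 1 marks Day 1 as baseline.
- SAP 5.7.2 uses the short phrase for Day 1: "The start and stop day of the AE relative to the first dose of IMP will be calculated as per Section 5.1.2". Section 5.1.2 in turn says that Day 1 "will be taken from 'Date of first dose of IMP in Treatment Period' on the Randomization CRF".
- The shorthand is not uniform. SAP 5.8.1 refers to the first dose of each period separately, so the phrase alone does not settle the matter.

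**ECG: effect of one tracing instead of the mean of three**

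Let v be the visit-to-visit SD and r the within-visit replicate SD, with a single post-baseline tracing.

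- SD of change with one baseline tracing: sqrt(2v^2 + 2r^2).
- SD of change with the mean of three: sqrt(2v^2 + 4r^2/3).
- Replicate part alone: 1.41r against 1.15r, a variance lower by 1 - (4/3)/2 = one third.
- The documents give neither SD. For assumed values in ms: (v, r) = (8, 8) gives 16.0 against 14.6, ratio 0.913; (6, 10) gives ratio 0.869; (10, 6) gives ratio 0.955. The SD of change falls by 4.5% to 13.1%.

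**ECG: flags**

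SAP Appendix 2 flags QTc above 500, and SAP 5.7.4.2 counts participants with at least one post-baseline flag. Take three repeated tracings of 506, 490 and 488 ms (illustrative). If each counts, the participant is flagged above 500. If they are averaged, (506 + 490 + 488)/3 = 494.7 and the participant is not.

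**The case against.** The strongest reply on labs is that the intent is already clear. SAP 5.1.3.1 covers clinic visit-based endpoints, protocol 13.6.4.4 separates screening from baseline, and the repeated-sample sentence can be read as choosing among repeats without naming a different visit. The literal result is also odd: repeating a Visit 3 sample would discard both Visit 3 values. All of this stands. A reader might infer that the SAP has deliberately set a pre-run-in laboratory baseline, and the documents do not support that. What remains is a stated rule that gives the wrong value when followed exactly.

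The harm also depends on a chain: a repeated sample, a marked Day 1 rise, and a programmer who puts this sentence above the general definition. A reader might take 2-28% as the chance of an error in this trial, but it is only a conditional figure on assumed rates. The liver listing in SAP 5.7.3.1 shows baseline and visit results together, so an affected case would be visible.

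On ECG, a reader might infer that nothing supplied says how the triplicates are combined. That is not so: protocol 6.2.15 averages three QTcF readings at screening or randomization, and the discontinuation criterion also averages three. Those rules do not extend to the SAP's summaries or to the other four parameters. The SAP does state averaging elsewhere: duplicate heights or weights in SAP 5.7.3.1 are averaged. The unsupplied manual may already contain the ECG rule. The noise also affects no planned treatment comparison, because SAP 5.7.4.2 plans summaries only, without confidence intervals for QTcF differences.

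**Conclusion.** Both points hold as minor clarifications that affect descriptive safety tables only.

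**Labs (high confidence).** The sentence conflicts with SAP 5.1.3.1 and protocol 13.4. Day 1 is the intended baseline, so this is a wording error. Followed literally, it would mix two baseline visits in the same tables for an assumed 4-16 of 80 participants, with well under one wrongly flagged liver case expected (0.02-0.32).

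**ECG (lower confidence, because the manual was not seen).** The SAP does not say how the baseline triplicate is reduced for summaries and change from baseline, and its general rule read literally keeps one tracing. That adds noise, raising the SD of change relative to averaging, but no bias between arms, because the same rule applies to every group. Flag counts also depend on how repeated post-baseline tracings are handled.

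**What to change.** 1. In SAP 5.7.3.1, add *in the treatment period* to the end of the repeated-sample sentence, so that it matches SAP 5.1.3.1 and protocol 13.4.
2. In SAP 5.7.4.2, define the ECG baseline for each parameter as the mean of the baseline triplicate, and state how repeated post-baseline tracings are combined for summaries and for flags. If the ECG manual already sets this, a citation is enough.

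The cost is a few words in two SAP sections. No new data are needed, since the triplicate tracings are already collected.

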5.7.3.2 Serology

Serology is assessed at Visit 1 and will be listed only.

5.7.3.3 Urinalysis

Urinalysis is assessed at Visits 1, 3, 4, 6 and 7 and will be listed only.

5.7.3.4 Drug Screen

A drug screen is performed at Visits 1, 3 and 7. Results will be summarized by treatment group for each parameter and visit for the safety analysis set.

5.7.3.5 Pregnancy Test

Pregnancy test results will be summarized by treatment group and visit for the safety analysis set.

5.7.4 Vital Signs, Other Physical Findings and Other Safety Data

5.7.4.1 Vital Signs

Summaries will be presented by treatment group for each vital sign parameter at each visit for the treatment period. Change from baseline to each post-baseline visit will also be presented for the treatment period.

Based on the criteria presented in Section 8, clinically significant changes from baseline in vital signs measurements (except waist circumference) and other defined flagged values will be identified at each visit. The number of participants with a clinically significant change from baseline will be summarized for the treatment period by parameter, visit and treatment group. The number of participants with at least one post-baseline flagged vital sign parameter value will be summarized by parameter, flagged criteria and treatment group.

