- 6.2.14 One or more laboratory values outside the normal range, based on the blood or urine samples taken at the screening visit, that are considered by the investigator to be clinically significant; or the participant has impaired hepatic function at screening, defined as serum alanine aminotransferase (ALT) or aspartate aminotransferase (AST) > 2 × upper limit of normal (ULN) or total bilirubin (TBL) > 1.5 × ULN or international normalized ratio (INR) > 1.2 (TBL ULN parameter not applicable for participants diagnosed with Gilbert's disease). Note: Out-of-range laboratory values should be confirmed on retest within the allowed screening window.
- 6.2.15 Clinically relevant abnormalities in the ECG measured at screening or randomization (including QT interval with Fridericia correction [QTcF] > 450 msec for males and > 470 msec for females, average of 3 measurements).
- 6.2.16 Positive serology panel (including hepatitis B surface antigen [HBsAg] and/or confirmed current hepatitis C infection [positive hepatitis C virus {HCV} antibody confirmed with reflex HCV RNA test]) and/or positive human immunodeficiency virus (HIV) antibody/p24 antigen screens.

Study Code: GWAP19030

EudraCT Number: 2019-003369-16 Clinical Protocol Global V3, 23Mar2021

- 6.2.17 Male and fertile (i.e., after puberty unless permanently sterile by bilateral orchidectomy) and with a partner of childbearing potential unless agree to ensure that they use male contraception (e.g., condom) or remain sexually abstinent during the trial and for 3 months after the last dose.
- 6.2.18 Female of childbearing potential (i.e., following menarche until becoming postmenopausal for ≥ 12 consecutive months unless permanently sterile by hysterectomy, bilateral salpingectomy, or bilateral oophorectomy) unless agree to use highly effective contraception (e.g., combined [estrogen and progestogen containing] hormonal contraception associated with inhibition of ovulation [oral, intravaginal or transdermal], progestogen-only hormonal contraception associated with inhibition of ovulation [oral, injectable or implantable], intrauterine devices/hormone-releasing systems, bilateral tubal occlusion, vasectomized partner [provided partner is the sole sexual partner and has received medical assessment of the surgical success], true sexual abstinence) during the trial (i.e., from screening) and for 3 months after the last dose.

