5.7.4.2 Electrocardiogram

An ECG will be performed at Visits 1, 3, and 7. Summaries will be presented for ventricular rate, PR interval, QRS duration, QT interval and QTcF by treatment group at each visit. Change from baseline to Day 85 will also be presented.

Based on the criteria presented in Section 8, defined flagged values will be identified at each visit. The number of participants with at least one post-baseline flagged ECG parameter value will be summarized for the treatment period by parameter, flagged criteria and treatment group.

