Appendix 2 Defined Flagged Values in ECG Parameters

Defined flagged values that will be used to identify low or high ECG parameters (See Section 5.7.4.2) are presented in [Table 6](#).

Table 6 Defined Flagged Values for ECG Parameters

ECG Parameter	Flag
QTc	> 450, > 480, > 500

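### Vital sign and ECG flag tables count any flagged post-baseline value, so abnormalities already present at baseline (for QTc, only the > 450 cut in women) are mixed with new ones

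*SAP*

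**What the plan says.** **Counting rule.** For vital signs, SAP 5.7.4.1 says: "The number of participants with at least one post-baseline flagged vital sign parameter value will be summarized". For ECG, SAP 5.7.4.2 says: "The number of participants with at least one post-baseline flagged ECG parameter value will be summarized for the treatment period". The outputs are Tables 14.3.8.3 and 14.3.8.5, both titled as incidence of flagged values (SAP Appendix 4).

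**Cuts.** SAP Table 5 uses absolute vital sign limits, for example systolic pressure above 140 or 160 and heart rate below 60 or above 100. SAP Table 6 flags QTc at "> 450, > 480, > 500", the same for both sexes. It does not name the correction, although 5.7.4.2 summarizes QTcF.

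**A different rule for liver tests.** In SAP 5.7.3.1, "treatment emergent is defined as criteria not met at baseline but met at any time post-baseline".

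**Protocol limits.** Section 6.2 (6.2.15) excludes QTcF "> 450 msec for males and > 470 msec for females, average of 3 measurements". Section 10 lists a QTcF of 500 ms or more (average of 3 measurements) among the criteria for permanent discontinuation. Sections 6.1 and 6.2 set no numeric limit on blood pressure, heart rate, temperature or respiratory rate.

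**Baseline-relative outputs that are planned.** SAP 5.7.4.1 plans change from baseline by visit and a count of clinically significant changes (Table 14.3.8.2). The criteria in SAP Table 4 cover blood pressure, heart rate and weight. SAP 5.7.4.2 plans ECG change from baseline to Day 85.

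**The concern.** A safety table titled as incidence is normally read as new on-treatment findings. A participant who enters with a heart rate of 55 or a systolic pressure of 145, and stays there, is counted exactly like one who moved there after dosing. The table does not let the reader separate the two.

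Efficacy has no formal hypothesis test (SAP 5.5.1), so descriptive safety tables are a large part of what this terminated trial reports. If 80 randomized participants (SAP 3.2) divided in the planned 2:2:1:1 ratio, each active arm and pooled placebo has about 80 × 2/6 = 26.7 people. At that size a few carried-over flags in one arm are visible. They can look like a drug effect or hide one.

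**Working it through.** The plan states no figure that depends on this rule, so there is nothing to reproduce. The check sets the rules side by side and then illustrates the size.

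**1. Where can a flag already exist at baseline?**

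*Vital signs.* At every cut in Table 5, because eligibility sets no numeric limit on those parameters.

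*QTc.* Applying the SAP cuts and the protocol limits to whole-millisecond values:

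| QTcF (ms) | SAP flags met | Man eligible on QTcF | Woman eligible on QTcF | Meets ≥ 500 |
|---|---|---|---|---|
| 450 | none | yes | yes | no |
| 451–470 | > 450 | no | yes | no |
| 471–480 | > 450 | no | no | no |
| 481–499 | > 450, > 480 | no | no | no |
| 500 | > 450, > 480 | no | no | yes |
| 501 | all three | no | no | yes |

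Barring eligibility deviations, the only QTc flag that can be carried over is > 450 in women at 451 to 470 ms. Protocol Appendix 1, footnote h, words the limits as strictly below 450 and 470, which would move only the boundary value.

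**2. What do the other outputs recover?**

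| Parameter | Flag table | Categorical change criterion (SAP Table 4) | Other baseline-relative output |
|---|---|---|---|
| Blood pressure, heart rate | yes | yes | change by visit |
| Temperature, respiratory rate | yes | no | change by visit |
| QTc | yes | no | change to Day 85 |

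No baseline-by-post-baseline shift table is listed for vital signs or ECG. A mean change does not show which flagged participants were already flagged.

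**3. How large could the carried-over share be?** This is an illustration with no drug effect. All means, SDs and correlations are assumptions; none comes from the documents.

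Model: Y_j = μ + σ(√ρ·u + √(1−ρ)·e_j), with u and e_j independent standard normal, j = 0 at baseline and j = 1…k afterwards. With cut c:

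- Any = P(max Y_1…Y_k > c)
- New = P(max Y_1…Y_k > c and Y_0 ≤ c)
- Carried-over share = 1 − New/Any

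For QTcF, all probabilities are conditional on Y_0 ≤ 470.

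Systolic pressure above 140, σ = 14, k = 4 (Visits 4 to 7):

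| μ | ρ | Any | New | Carried over |
|---|---|---|---|---|
| 120 | 0.5 | 20.7% | 16.0% | 23% |
| 120 | 0.7 | 17.4% | 11.6% | 33% |
| 125 | 0.5 | 34.3% | 24.0% | 30% |
| 125 | 0.7 | 28.9% | 17.4% | 40% |
| 130 | 0.5 | 50.3% | 31.0% | 38% |
| 130 | 0.7 | 43.4% | 22.8% | 48% |

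For example, at μ = 125 and ρ = 0.5, an arm of 27 shows 27 × 0.343 = 9.3 flagged participants on average, of whom 27 × 0.240 = 6.5 are new.

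Women, QTcF above 450, σ = 18, k = 1 (Visit 7 only), μ from 415 to 435, ρ from 0.6 to 0.8: Any is 2.5% to 19%, New is 1.4% to 10%, and 23% to 60% of those flagged are carried over. For eligible men the carried-over share is 0%.

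**4. The 500 ms boundary.** The table in step 1 shows that exactly 500 ms meets the protocol criterion but misses the SAP's top category. This is an undercount at one value. It is separate from the baseline question.

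**The case against.** The case against is substantial.

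- **The tables are descriptive and literally described.** The SAP text speaks of post-baseline flagged values, not treatment-emergent ones, and the liver rule is defined for one table. That is true, but the table titles still invite the stronger reading.
- **Change outputs already exist.** For blood pressure and heart rate, Table 14.3.8.2 is a baseline-relative count. For ECG there is change to Day 85, and with one scheduled post-baseline ECG the listings allow each woman above 450 to be checked. This stands as a partial offset. A reader might infer that ECG has no baseline-relative output at all; the SAP does not support that. Only a categorical or shift table is missing.
- **Randomization protects the comparison on average.** This stands. Carried-over flags inflate all arms alike in expectation.
- **A reporting flag need not copy a stopping rule,** which here uses an average of 3 measurements. That is fair, but a one-value mismatch serves no evident purpose.

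Two further inferences are tempting and fail. The first is that the QTc cuts in general import baseline values: eligibility rules this out for men, and at 480 and 500 for both sexes. The > 500 boundary cannot import them either, since it only omits exactly 500.

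The second is to measure the harm by how often two small arms differ by chance. For two independent Binomial(27, q) counts, the probability of a difference of 4 or more is 21% at q = 0.174 and 34% at q = 0.503 (the lowest and highest Any values above). It is 13% at q = 0.116 and 30% at q = 0.310 (the lowest and highest New values). Most of that is ordinary small-sample noise, which a treatment-emergent count shares, so it does not measure this defect.

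**Conclusion.** The point holds in a limited form. The flag counts in SAP 5.7.4.1 and 5.7.4.2 have no baseline condition, and their tables are titled as incidence. Pre-existing and new vital sign abnormalities are mixed at every cut in Table 5. For QTc the mixing is confined to the > 450 cut in women eligible at 451 to 470 ms. The gap is widest for temperature and respiratory rate, which have no change criterion, and for ECG, which has no categorical change or shift table.

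There is no average bias between arms. The cost is a less readable table and, with 80 randomized, a comparison that chance baseline imbalance can blur. The carried-over shares above (23% to 48% for systolic pressure, 23% to 60% for QTcF in women) depend wholly on assumed distributions and show only that the share need not be trivial. Importance is minor. The unnamed QT correction and the 500 ms boundary are separate inconsistencies to be cleared up at the same time.

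**What to change.** - Apply the SAP's liver rule, cut by cut, to Tables 14.3.8.3 and 14.3.8.5: count a participant when the flag is absent at baseline and present afterwards. Keep the any-value count as a second column, because the new rule hides worsening within a band.
- Show the lowest QTc cut by sex, using the protocol's own eligibility limits.
- Name QTcF in SAP Table 6.
- Reconcile the SAP's > 500 reporting flag with the protocol's ≥ 500 criterion. This review takes no view on the clinical threshold.

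The cost is one extra column per table, a split by sex for one cut, and minor programming. No new data are needed: baseline values are collected, and the SAP already plans to identify flags at each visit. The treatment-emergent column will still contain chance crossings of a cut (12% to 31% of participants in the systolic illustration, with no drug effect), so it should be read against placebo.
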